**Youth FORWARD scale-up study AIM 3:**

**AIM 3 (Clinical Effectiveness):** To compare clinical effectiveness of YRI when delivered via the EPP platform to results of our previous randomized control trial (RCT) of YRI as measured by improved mental health and reduced functional impairments among high-risk youth. Emotion regulation will be examined as a major mechanism by which the YRI improves behavior of treated youth and their functioning in the ENTR.

*Hypothesis 3(a): Participants who are exposed to YRI will demonstrate greater reduction in mental health and functional problems than participants who do not receive the YRI intervention; emotion regulation (as measured using the Disturbances in Emotion Regulation Scale) will operate as a major mechanism of YRI improvements; high comorbidity will be a treatment modifier.*

*Hypothesis 3(b): Improvements in mental health and functioning due to YRI will lead to (mediate) greater employment outcomes and superior economic self-sufficiency over time.*

*Hypothesis 3(c): Homelessness, orphanhood, young parenthood, and high problems in emotion regulation comorbid with other mental health conditions will be moderators lessening the effectiveness of YRI.*

The table below outlines study primary outcomes, primary predictors, moderators and hypothesized mediators.

Primary Outcome Variables
Difficulties in Emotion Regulation (DERS)
Hopkins Symptom Checklist (HSCL)
Oxford Measure of Psychosocial Adjustment (OMPA)
Employment
Economic Self-Sufficiency
Primary Predictor Variables
Time
Group Membership (ENTR-only, YRI+ENTR, Control)
Possible Moderators
Gender
Age

Education Level
Literacy
Session Attendance
Hypothesized Mediators
Emotion regulation (DERS)
Oxford Measure of Psychosocial Adjustment (OMPA)
Hopkins Symptom Checklist (HSCL)
WHO Disability Assessment Scheduled (WHODAS)

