The goal of this analysis is to determine if there are differences among the three groups assigned at randomization (Control, ENTR, and ENTR+YRI). As described above, all analyses will include the aggregated baseline value of the outcome as a control at the cluster level, and furthermore, of any cluster-level potential treatment confounders shown to be imbalanced across the three groups. In particular we will be looking for group differences in the slopes of the primary outcomes over the lifetime of the study. Fixed effects will be time and group membership and their two-way interaction. Each subject will be measured three times—baseline, post-training, and at 12-month follow up—so we have three repeated measures for each subject, and each set of repeated measures is nested within study cluster. Subject- and cluster-specific slopes and intercepts will be modeled as random effects. We can test for the necessity of the subject and cluster specific slopes through likelihood ratio tests. Evidence of a group differential effects will be if the likelihood ratio test for the time by group interaction is significant at the 0.05 level. For pairwise differences we will examine the regression coefficients and base inference on Wald tests. We will estimate the model with Restricted Maximum Likelihood (REML, also MLR) for testing for random effect parameters and Full Maximum Likelihood (FML or MLF) for fixed effects. We will account for attrition by calculating inverse probability weights and/or multiple imputation. All linear modeling assumptions will be verified, both by

evaluating underlying distributions and model residuals. Approaches to the violation of model assumptions or for non-continuous outcomes include use of response transformations, generalized linear mixed effect models or generalized estimating equations.

We now expand the above model to include possible effect modifiers gender, mental health status at baseline. To the model above we will include a three-way interaction between time, gender, and treatment group. Evidence of a moderating effect will be if likelihood ratio test for the three-way interaction term is significant at the 0.05 level.

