### **Data Analysis Plan for Hypothesis 3c:**

*Hypothesis 3(c): Homelessness, orphanhood, young parenthood, and high problems in emotion regulation comorbid with other mental health conditions will be moderators lessening the effectiveness of YRI.*

**Primary Outcome:** Measures of employment and superior economic sufficiency

**Primary Predictor:** Group Membership

**Mediator:** Mental Health

**Possible Moderators:** Subject gender, age, education level/literacy, session attendance, emotion regulation.

To the mediation model described in hypothesis 3b we will add terms to account for the moderating influences of gender, age, education level/literacy, session attendance, and emotion regulation. For purposes of exposition we will generically label the moderator as  $W$ . Our hypothesis is that moderators act on the influence of group membership and mental health. The conditional process equations in this case are (only one moderator was included for brevity):

$$MH(12\ months) = B_0 + a * X$$

$$Employment = B_0 + B_0 + cX + b_1 * MH + b_2 * G + b_3 * G * MH$$

In these equations the indirect effect of group membership on employment and economic self-sufficiency is  $(a_1 + a_3 * W) * b$ . The value  $a_3 * W * b$  is sometimes called the index of moderated mediation. In the case of dichotomous  $W$  (gender, homelessness, young parenthood) this value reduces to  $a_3 * b$  and is interpreted as the difference of the indirect effect of group membership on employment and economic self-sufficiency of the two  $W$  groups. Test for moderation can be directly from the coefficient  $a_3$ . Alternative tactics include SEM as opposed to conditional process equations. KHB rescaling will be needed since moderators, mediators, and outcomes represent different variable types (binary, continuous etc.). In practice we can include all moderators in the model simultaneously.

We can also verify which path the candidate variables modify (we assumed the path from primary predictor to mediator). This can be done in the context of SEM models. We can fit models where the moderators act on the paths from mediator to outcome or both. Using fit indices such RMSEA we can compare model fits to determine which model best matches the data.

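### RMSEA is the only criterion named for locating moderation in Hypothesis 3c; it measures overall misfit, so the path it selects can reflect coding, product-term handling or chance

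*Combined protocol and SAP*

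**What the plan says.** The section on Hypothesis 3c in the combined protocol and SAP sets out a moderated mediation model. Group is X, mental health (MH) is the mediator, employment or economic self-sufficiency is the outcome, and W is a generic moderator. The text takes the first stage (X to MH) as the moderated path and offers a direct check of a_3: "Test for moderation can be directly from the coefficient".

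It then opens the question of where moderation acts: "We can also verify which path the candidate variables modify (we assumed the path from primary predictor to mediator". The rivals are the second stage and both stages: "We can fit models where the moderators act on the paths from mediator to outcome or both". The choice among them is made by fit: "Using fit indices such RMSEA we can compare model fits to determine which model best matches the data". RMSEA is the only index named.

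The section gives no cut-off, tie rule, no-moderation candidate, common variable set, coding or centring, and no rule for handling product terms. Its examples of dichotomous moderators are "gender, homelessness, young parenthood". Group has three levels, "Group Membership (ENTR-only, YRI+ENTR, Control", so X×W is two terms.

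The printed outcome equation is "Employment = B_0 + B_0 + cX + b_1 * MH + b_2 * G + b_3 * G * MH". It places the interaction on the second stage, and the printed mediator equation has no a_3 term, although the indirect-effect formula uses a_3.

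**The concern.** RMSEA summarises how far a whole model is from the observed covariances, per degree of freedom. Which path W modifies is a question about two coefficients, a_3 and b_3. A model can have a low or high RMSEA for reasons unrelated to either. In product-term models these reasons include whether X×W has a direct path to the outcome, and whether MH×W is allowed to covary with the MH residual.

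At stake is the mechanism reported under Hypothesis 3c. One reading is that, say, homelessness blunts the effect of YRI on mental health. The other is that it weakens the link from mental health to employment. If software defaults or 0/1 coding decide between them, the paper may name the wrong one. The false discovery rate adjustment planned under Multiple Comparisons gives no protection here, because it acts on p-values and a ranking by RMSEA has none.

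**Working it through.** **Inputs.** The documents state no sample size, effect size or RMSEA threshold, so there is no figure to reproduce. The following are assumptions: N = 400 and 1200; three equal arms; binary W at 50%; continuous MH and outcome with residual SD 1; no clustering; a_3 = 0 or −0.3; b_3 = 0 or −0.2; 1000 replicates. The four truths are none, first-stage, second-stage and both.

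**Formula.** RMSEA = √[max(χ² − df, 0) / (df × N)], with χ² from maximum likelihood for observed-variable path models.

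**Degrees of freedom with three arms.** With a common variable set and MH×W exogenous:
- First-stage: MH×W is omitted from the MH equation (1), and two X×W terms and MH×W from the outcome equation (3), so df = 4.
- Second-stage: 3 + 2 = 5.
- Both: 1 + 2 = 3.

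With each model carrying only its own product terms, df = 2, 1 and 3.

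**One simulated data set, four set-ups.** Each cell gives χ², df and RMSEA. N = 400, since 299.98 / (4 × 0.433²) = 400.

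| Set-up | First | Second | Both | Lowest |
|---|---|---|---|---|
| 0/1, common set | 303.98, 4, 0.433 | 304.29, 5, 0.387 | 303.55, 3, 0.500 | second |
| 0/1, own terms | 5.97, 2, 0.070 | 293.62, 1, 0.855 | 303.55, 3, 0.500 | first |
| Centred, common set | 6.65, 4, 0.041 | 6.95, 5, 0.031 | 6.22, 3, 0.052 | second |
| Centred, own terms | 5.97, 2, 0.070 | 0.37, 1, 0.000 | 6.22, 3, 0.052 | second |

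The data are the same in every row. With own terms, coding alone moves the choice from first-stage to second-stage.

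The common-set rows show why. Going from centred to 0/1 coding adds the same amount to each χ²: 303.98 − 6.65 = 297.33, 304.29 − 6.95 = 297.34 and 303.55 − 6.22 = 297.33 (equal up to rounding). This is the forced association of MH×W with MH. Once it dominates, the model with most degrees of freedom has the lowest RMSEA. With own terms the first-stage model contains no MH×W, so it escapes the penalty.

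**Selection by RMSEA, N = 1200 (% of runs).**

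| Set-up | Truth | First | Second | Both | Tie |
|---|---|---|---|---|---|
| 0/1, own terms | each of the four | 100 | 0 | 0 | 0 |
| 0/1, common set | each of the four | 0 | 100 | 0 | 0 |
| Centred, own terms | first | 32 | 17 | – | – |
| Centred, own terms | second | 28 | 16 | 5 | 51 |
| Centred, own terms | both | 31 | 19 | 3 | 47 |
| Common set, MH×W–MH residual covariance free | first | 28 | 4.5 | 14 | 54 |
| As above | second | 0.1 | 32 | 20 | 48 |
| As above | both | 0.3 | 10.5 | 78 | 11 |

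(A dash marks a share not reported.) In the last set-up df = 3, 4 and 2, and the results are identical under raw and centred coding. At N = 400 it separates the paths less well: with first-stage true it picks first in 18%, second in 13% and ties in 60%.

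**No moderation, N = 1200.** With centred coding and own terms RMSEA still names the first or second stage alone in 26% + 18% = 44% of runs. It cannot report none, because that model is not a candidate.

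**Two-group model split by W, other paths free.** The both-paths model is saturated, so its RMSEA is 0 by construction and it always wins or ties.

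**Comparator.** Likelihood ratio tests of a_3 (2 df) and b_3 (1 df) at 0.05 do not depend on coding. With no moderation they find neither path in 89% (N = 400) and 90% (N = 1200) of runs, close to 0.95² = 0.90. At N = 1200 they identify the correct single path in 55% (first) and 87% (second), and both in 57% when both are true.

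**The case against.** The strongest reply has three parts.

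First, RMSEA is an example and the step is worded as something the team can do. First-stage moderation is declared in advance, and a_3 is to be tested directly. This stands. A reader might infer that the main Hypothesis 3c result rests on RMSEA, and the documents do not support that. But RMSEA is still the only stated means of locating moderation, and the section offers no test of b_3. Elsewhere the plan does test moderation directly. For Hypothesis 3a it says "Evidence of a moderating effect will be if likelihood ratio test for the three-way interaction term is significant at the 0.05 level".

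Second, a reader might infer that RMSEA carries no information about the path, or that the second-stage model always misfits. Neither holds. With a common variable set and the residual covariance freed, RMSEA responds to the truth and does not depend on coding. Centring with a common set also helps: with second-stage moderation true at N = 1200, it picks second in 41% and first in 0.3%. With 0/1 coding on a common set it is the second-stage model that always wins.

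Third, the set-ups that give 100% are assumed, because the section does not say how product terms enter. That is true, and it limits the figures to those set-ups. It also means that nothing in the plan rules them out.

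**Conclusion.** The concern holds in a limited form. As written, the criterion can return a site of moderation that reflects coding, the handling of product terms or chance. Depending on choices the plan leaves open, it picks first-stage always, second-stage always, or nearly independently of the truth. In the favourable specification it is weakly informative, with about half of runs tied at N = 1200 when one path is moderated.

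The percentages rest on the assumed N, effects, 50% prevalence, continuous variables and absence of clustering. The mechanism does not rest on the exact values: under 0/1 coding with MH×W exogenous, the result was 100% under all four truths.

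This bears on a secondary, optional check and on the mechanism conclusion of Hypothesis 3c. It does not touch the comparison of arms. It should be corrected before analysis.

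**What to change.** 1. Keep first-stage moderation (a_3) as the pre-specified Hypothesis 3c model. Reconcile the printed equations, which show an interaction of G with MH, with the a_3 formula in the text.
2. To examine the path, fit one joint model: X×W (two terms for three arms) in the MH equation, and X×W and MH×W in the outcome equation. State the coding and centring of W and of the arm indicators, and how product terms are handled.
3. Report each interaction with its interval and a likelihood ratio or bootstrap test that accounts for clustering, under the planned false discovery rate adjustment. No moderation is then a possible result.
4. Compare only nested models on the same variables, and use RMSEA for overall fit only.
5. Label any path other than first-stage as exploratory.

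The cost is SAP wording and slightly wider intervals than a single-path model. The direct tests may often be inconclusive if effects are small (55% correct for a_3 = −0.3 at N = 1200 in the simulation), but they show that uncertainty, which a ranking by RMSEA hides.

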## **Part II Emotion Regulation as the Mechanism Through which the YRI improvements operate**

**Primary Outcomes:** OMPA internalizing, OMPA externalizing

**Primary Predictor:** Group Membership (Control, ENTR-only, YRI+ENTR)

**Hypothesized Mediator:** Emotion Regulation (assessed by DERS)

**Possible Moderators:** Subject gender, age, education level/literacy, session attendance

We hypothesize that the YRI improvements may operate through changes in emotion regulation. This is a proposed mediation model where the primary predictor is group membership, the primary outcome is mental health at 12 months, and the mediator is emotion regulation as measured by the Difficulties in Emotion Regulation (DERS) at six weeks. We will test for the indirect effect of group membership on Mental Health Status using conditional process analysis (Hayes, 2013). The conditional process equations are (if gender modifies the indirect effect for example):

$$DERS(6\ weeks) = B_0 + a * X$$

$$MH(12\ months) = B_0 + cX + b_1 * DERS(6\ weeks) + b_2 * G + b_3 * G * DERS.$$

Where  $X$  is group membership and  $G$  is gender. The coefficient  $a$  quantifies the effect of group membership on emotion regulation and  $b$  quantifies the effect emotion regulation on mental health independent of group membership. The product  $p = a(b_1 + b_3 * G)$  is the *indirect effect* of group membership on Mental Health. We can test for the significance (null hypothesis  $p = 0$ ) via

bootstrapping. A significant (at 0.05) is indication that emotion regulation mediates the relationship between the YRI effects and mental health. For outcomes that are binary we will need to use the KHB method (Breen, Karlson, & Holm, 2013) to rescale the regression coefficients correctly. A strength of this analysis is that group membership, emotion dysregulation and Mental Health are measured at three different time points which is necessary for causal mediation (though not sufficient).

As an alternative we can test for mediation using Structural Equation Modeling (SEM). This approach is more flexible than conditional process analysis and may allow us to use full-information maximum likelihood (FIML) as opposed to multiple imputation. All causal models will be evaluated for the possible effects of unmeasured confounders (VanderWeele & Ding, 2017).

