**Missing Data:** Using ITT principle we will obtain estimates of missing values of all study participants and at all time points. We will primarily use multiple imputations through chained equations. Missing data may exist at items within scales and we will use the Plumptre method (ref needed). Furthermore, where supported by our software, we can combine the use of imputations with attrition weighting. We will report both percentage of missing data and percentage of complete cases. For SEM models we can employ FIML to address missingness .

**Multiple Comparisons:** We will use False Discovery Rate (FDR) (ref needed) to adjust for multiple comparisons within hypothesis. This is necessary since we will be comparing multiple models.

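### The primary imputation method is not tied to the interactions the plan tests; unless it carries them, moderator estimates shrink toward zero roughly in proportion to the fraction missing

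*Combined protocol and SAP*

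**What the plan says.** The Missing Data paragraph, which follows the plan for Hypothesis 3c, sets the scope: "Using ITT principle we will obtain estimates of missing values of all study participants and at all time points". It names the main method: "We will primarily use multiple imputations through chained equations". It gives no variable list, no product terms and no imputation by arm or by moderator.

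Other routes are allowed. The plan for Hypothesis 3a says "We will account for attrition by calculating inverse probability weights and/or multiple imputation". The Missing Data paragraph adds "Furthermore, where supported by our software, we can combine the use of imputations with attrition weighting" and "For SEM models we can employ FIML to address missingness".

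The moderation analyses are interactions:

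- Hypothesis 3a: "To the model above we will include a three-way interaction between time, gender, and treatment group". The criterion is "Evidence of a moderating effect will be if likelihood ratio test for the three-way interaction term is significant at the 0.05 level". Baseline mental health status is also named as a modifier.
- Part II (emotion regulation as mechanism): the coefficient b3 on G × DERS enters the indirect effect a(b1 + b3·G). Gender is given as an illustration ("if gender modifies the indirect effect for example").
- Hypothesis 3b: the same structure, with G × mental health in the employment equation.
- Hypothesis 3c: the text uses a3, the group-by-moderator coefficient, as the direct test of moderation.

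**The concern.** Multiple imputation reproduces in the missing values only the relations that its own model contains. Chained equations as usually set up hold main effects only. If an interaction is in the analysis model but not in the imputation model, the completed data mix observed youth, who show the moderation, with imputed youth, who show little or none of it.

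The error runs one way, toward reporting no moderation, and the results would give no sign of it. It adds to the information already lost through dropout. Moderation is part of Hypothesis 3a and the whole of Hypothesis 3c. By contrast, the Hypothesis 3a mixed model, fitted by likelihood to the observed waves, would not have this bias when only outcomes are missing at random. An unspecified imputation step could therefore leave the moderator test worse off than no imputation.

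**Working it through.** **Inputs.** From the plan: the method and its scope, and the interactions listed above. The plan states no sample size, effect size or attrition rate, so there is no figure of its own to reproduce. Assumed: dropout d of 5, 10, 20 and 30%.

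**Algebra.** Let Δ be the true gender-by-YRI interaction at the last wave (a difference of differences against control), and let a fraction d of last-wave values be missing at random. A main-effects imputation model has a difference of differences of zero by construction. The pooled estimate is then

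(1 − d)·Δ + d·0 = (1 − d)·Δ,

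which is 0.95, 0.90, 0.80 and 0.70 of Δ at the four dropout levels.

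If the gender effect is already present in the post-training measure, that measure carries part of it into the imputed values. In the simulation below, the post-training measure enters the last wave with coefficient 0.3, both interactions are 0.40, and half of leavers have a post-training value. The share retained among leavers is 0.5 × (0.3 × 0.40)/0.40 = 0.15. The ratio becomes (1 − d) + 0.15d = 1 − 0.85d, or 0.96, 0.92, 0.83 and 0.75.

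**Simulation.** Assumptions: 1200 youth in three equal arms; binary gender; baseline, post-training and 12-month waves; dropout completely at random; half of leavers also missing the post-training (DERS) measure; 5 imputations; 300 replicates per setting; no clustering. Entries are estimated over true interaction. Ranges cover the gender effect being absent from, or present in, the post-training measure; the last column also spans both terms.

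| Assumed d | 1 − d | Gender × YRI, main-effects imputation | G × DERS, main-effects imputation | Both terms, interactions in imputation |
|---|---|---|---|---|
| 5% | 0.95 | 0.91–0.96 | 0.92–0.97 | 0.99–1.03 |
| 10% | 0.90 | 0.90–0.93 | 0.88–0.92 | 0.98–1.01 |
| 20% | 0.80 | 0.79–0.83 | 0.81 | 0.99–1.02 |
| 30% | 0.70 | 0.73–0.75 | 0.68–0.69 | 0.98–1.01 |

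Monte Carlo standard errors are 0.012 to 0.020, so differences of a few hundredths from the algebra are mostly simulation noise.

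**Repeats under other settings.**

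- Dropout dependent on baseline, true effect −0.30: main-effects imputation gave −0.28, −0.24 and −0.21 at 10, 20 and 30%, which is 0.93, 0.80 and 0.70 of the truth. Imputation with the interactions gave −0.30 to −0.31.
- 500 runs, true effect −0.30: −0.26, −0.23 and −0.21, or 0.87, 0.77 and 0.70.
- A further run gave 0.95, 0.89, 0.80 and 0.67 at 5, 10, 20 and 30%. Imputing within arm with the G × DERS product restored both terms to about 0.97–1.01.

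Across all runs the loss was 3–13% at 5–10% dropout and 17–33% at 20–30%.

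**Limits.** The simulated gender term is arm by gender at the last wave, standing in for time by gender by group. G × mental health and the Hypothesis 3c terms were not simulated; the algebra is the ground for extending the point to them.

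**The case against.** A reader might infer that the plan commits to main-effects imputation and that its moderator results will therefore be biased. The documents do not support that. They are silent on the imputation model, and main effects only is a statement about common software practice. This objection stands, and the point must be put conditionally.

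The plan also has routes on which the problem does not arise, or need not. Weighting alone imputes nothing. FIML avoids the shrinkage if the SEM includes the interactions. But both are offered as options, and chained equations are named as primary.

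Gender is not the moderator named in the hypotheses. Hypothesis 3a names high comorbidity; Hypothesis 3c names homelessness, orphanhood, young parenthood and emotion-regulation problems comorbid with other conditions. This also stands: the figures above illustrate the mechanism and do not estimate the effect on those moderators. The mechanism itself does not depend on which moderator is used.

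Finally, it might be inferred that the main time-by-group test is compromised. Nothing here shows that.

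**Conclusion.** The point holds in conditional form. The plan makes chained-equation imputation primary and does not link it to the interactions it tests. If those terms are left out, moderator estimates from imputed data are pulled toward zero by roughly the fraction missing: about 5–10% at assumed dropout of 5–10%, and about 20–33% at 20–30%. The first is minor; the second could turn a real moderator into a null finding. The true size cannot be fixed from the documents, because attrition is not stated and the imputation model is open. The change is worth making because the bias has one direction, would go unseen, and is cheap to prevent.

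**What to change.** Add to the Missing Data paragraph text to this effect:

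- Outcomes are imputed in wide format, one column per wave, separately within each randomised arm, with the baseline moderators in every equation. Each arm then has its own moderator coefficient at each wave, which preserves the arm-by-moderator-by-wave terms without listing them.
- Each equation also includes the moderator products that the matching analysis model needs, formed only from variables other than the one being imputed. Examples are G × DERS when imputing mental health, G × mental health when imputing DERS or employment, and G × employment when imputing mental health. A product must not sit in the equation for its own component.
- Alternatively, a substantive-model-compatible imputation method is used to the same end.
- Session attendance enters only in arms where sessions are delivered, since the control arm is untreated.

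The cost is SAP wording and a few lines of code, with no change to design or conduct. The downsides are slightly noisier imputations and, if a cluster term is carried, only about a third of the clusters in each imputation model. The plan itself already regards the total number of clusters as small.

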The Youth FORWARD Hybrid Type 2 Effectiveness-Implementation scale-up study proposes to implement and test an evidence-based intervention called the Youth Readiness Intervention (YRI) alongside the German Development Agency's (GIZ) Entrepreneurship Training program (ENTR) which is part of a larger youth Employment Promotion Programme (EPP). Youth who apply to the employment program are screened for eligibility and those youth who are deemed eligible are clustered and randomized into three study arms: ENTR-only, YRI+ENTR, Control. Below we outline our procedures for clustering youth as well as our detailed data analytic plan for addressing Study Aim 3, which regards clinical effectiveness of the YRI when delivered by an alternate delivery platform (ENTR).

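### The plan does not say whether its chained-equations imputation accounts for clusters; if it is run single-level, standard errors for the arm contrasts come out too small

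*Combined protocol and SAP*

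**What the plan says.** The opening paragraph sets out a cluster-randomized design: "those youth who are deemed eligible are clustered and randomized into three study arms: ENTR-only, YRI+ENTR, Control". The Hypothesis 3a analysis plan recognises this. It notes that "each set of repeated measures is nested within study cluster" and specifies that "Subject- and cluster-specific slopes and intercepts will be modeled as random effects". It also lists Cluster ID as a strata indicator and puts a cluster-level baseline aggregate of the outcome into every analysis.

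The Missing Data paragraph sets the scope of imputation: "Using ITT principle we will obtain estimates of missing values of all study participants and at all time points". Outcomes are therefore imputed as well as covariates and items. The method is: "We will primarily use multiple imputations through chained equations". No imputation model follows. The paragraph does not say which variables enter, whether arm, cluster or earlier waves are among them, or how many imputations are drawn.

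Other approaches are allowed. The Hypothesis 3a plan says "We will account for attrition by calculating inverse probability weights and/or multiple imputation". The Missing Data paragraph adds that "where supported by our software, we can combine the use of imputations with attrition weighting" and that "For SEM models we can employ FIML to address missingness". None of these statements links imputation to the clusters.

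**The concern.** Chained equations in their ordinary form treat rows as independent given the predictors. An imputed outcome then carries none of its cluster's own effect beyond what the predictors convey. Mixing such values with observed ones pulls cluster means towards each other. The completed data show less between-cluster variance than the trial really has, and that variance sets the standard error of a cluster-randomized contrast.

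The analysis model does not repair this. Its cluster random effects are estimated from data in which part of the cluster correlation has been removed. Rubin's rules add variance for the imputation draws, but not the missing cluster component. At stake are standard errors and type I error for the arm comparisons, in a trial that itself describes its number of clusters as small.

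**Working it through.** **Inputs.** From the documents: clusters are randomized; outcomes are imputed at all waves; the test level is 0.05; the cluster baseline aggregate is in all analyses. Not in the documents: clusters per arm (k), youths per cluster (m), ICC (ρ), missing fraction (f), and the baseline–outcome correlation. The plan has no figure to reproduce, so everything below rests on assumed inputs. The calculations use a two-arm contrast, a simplification of the three-arm repeated-measures model.

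**Step 1: effect on the ICC.** Take total variance 1, outcomes missing completely at random, and an imputation model with arm but not cluster. Two youths in a cluster share its effect only if both are observed, so the ICC becomes (1 − f)²ρ. The multiplier is 0.9² = 0.81, 0.8² = 0.64 and 0.7² = 0.49 at 10%, 20% and 30% missing.

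**Step 2: effect on the standard error.** Per cluster:

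- True variance: ρ + (1 − ρ)/[m(1 − f)].
- Within-imputation variance: (1 − f)²ρ + (1 − f)(1 − ρ)/m + f/m.
- Between-imputation variance: f/m + f²/[m(1 − f)].

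The SE ratio is the square root of (within + between)/true. For ρ = 0.05, m = 40, f = 0.20:

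- Within: 0.032 + 0.019 + 0.005 = 0.056.
- Between: 0.005 + 0.00125 = 0.00625.
- True: 0.05 + 0.0296875 = 0.0796875.
- Ratio: 0.06225/0.0796875 = 0.78 in variance, 0.88 in SE.

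Over m = 10 to 60, the SE ratio runs from 0.99 (m = 10, ρ = 0.02, f = 0.10) to 0.77 (m = 60, ρ = 0.10, f = 0.30).

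**Step 3: simulation without covariates.** Settings: 2,000 trials each, k = 10 per arm, m = 40, 10 imputations, Rubin's rules, cluster-mean t test on 2k − 2 = 18 df.

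| ICC | Missing | ICC after imputation | SE / true SD | Type I error |
|---|---|---|---|---|
| 0.02 | 10% | 0.016 | 0.96 | 5.5% |
| 0.02 | 20% | 0.012 | 0.94 | 6.0% |
| 0.02 | 30% | 0.010 | 0.91 | 6.1% |
| 0.05 | 10% | 0.040 | 0.95 | 5.5% |
| 0.05 | 20% | 0.032 | 0.87 | 8.0% |
| 0.05 | 30% | 0.024 | 0.87 | 8.3% |
| 0.10 | 10% | 0.080 | 0.90 | 7.4% |
| 0.10 | 20% | 0.063 | 0.85 | 8.6% |
| 0.10 | 30% | 0.048 | 0.78 | 10.9% |

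With nothing missing, type I error was 4.7% to 5.3%.

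**Step 4: with the plan's own covariate.** The cluster baseline aggregate carries cluster information and should reduce the bias. Three sets of simulations put it in both imputation and analysis, with k = 10 per arm and single-level imputation.

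- *Baseline–outcome correlation 0.5 at both levels (3,000 trials per setting).* Variance was understated in all 18 settings. At ICC 0.02 the variance ratio was 0.82 to 0.93 and type I error 4.4% to 5.8%. With 40 youths per cluster: ICC 0.05 and 30% missing gave 0.71 and 7.4%; ICC 0.10 and 20% missing gave 0.74 and 7.8%; ICC 0.10 and 30% missing gave 0.64 and 9.9%.
- *Cluster effects correlated 0.7 to 0.9 (1,500 trials per setting, Monte Carlo error about 0.6 points).* The variance ratio was 0.70 to 0.97. Type I error was 4.3% to 4.5% at ICC 0.02, 10% missing, 20 per cluster; 4.7% to 5.0% at ICC 0.05, 20% missing, 20 per cluster; 5.4% to 6.1% at ICC 0.10, 30% missing, 20 per cluster; and 6.1% to 7.3% at ICC 0.10, 30% missing, 40 per cluster.
- *A further check.* The variance ratio was 0.63 to 0.94 and type I error about 4% to 9%, near nominal at ICC 0.02 and in several ICC 0.05 settings. Analysis of the available data, without imputation, stayed at 4.4% to 5.7%.

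**Step 5: cluster indicators as a remedy.** In the Step 3 setup, fixed cluster indicators in the imputation model removed the downward bias (SE / true SD 1.00 to 1.17) but overstated a low ICC (0.02 became 0.025 to 0.041) and were conservative (type I error 2.1% to 4.9%). A random-effects imputation model was not simulated.

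**The case against.** A reader might infer that the plan has chosen plain chained equations with no cluster term. It has not: the paragraph neither includes nor excludes cluster. Chained equations can carry cluster indicators or random effects, and the plan attends to clustering in its matching, its strata indicators and its mixed model. This stands. The defect is an unspecified imputation model, not a stated wrong one. Silence is still not inclusion. Cluster structure has to be added to chained equations deliberately, and the mediation equations for Hypotheses 3a to 3c show no cluster term either.

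A reader might also infer that type I error necessarily exceeds 5%. The documents do not support that. They give none of the quantities that determine it, the simulations are simpler than the planned time-by-group likelihood ratio test, and size is close to nominal in several settings once the baseline aggregate is used. What survives is the direction: estimated variance was below the true value throughout.

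Finally, weighting and full-information likelihood are permitted, and properly specified imputation is an accepted approach under missing at random that can use auxiliary variables. So imputing outcomes is not inherently worse than leaving them unimputed; the loss belongs to the single-level version. But imputation remains the main method named, and the permitted alternatives do not settle how it is specified.

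**Conclusion.** The concern holds in conditional form. The plan makes chained-equations imputation its main missing-data method and does not tie it to the cluster randomization or to its own cluster random effects. If the imputation is run single-level, as the text permits, standard errors for the arm contrasts are too small. With the baseline aggregate included and 10 clusters per arm assumed, the illustrative size is an estimated variance of about 0.63 to 0.94 of the true value. Type I error then runs from nominal (ICC 0.02, or little missing data) to about 9% at ICC 0.10, 30% missing and 40 youths per cluster. In that last setting the separate runs spanned 6.1% to 9.9%, depending mainly on how strongly baseline predicts outcome. These figures illustrate a simplified design and do not predict this trial's error rate. The change should be made: it is cheap, and without it the validity of the arm comparison may rest on a software default.

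**What to change.** In the Missing Data paragraph, state that imputation will use multilevel chained equations with at least a random cluster intercept, and with arm, all waves of the outcome and the cluster baseline aggregate as predictors. Add random cluster slopes or moderator interactions only where they are estimable; a small number of clusters may not support them. Fixed cluster indicators are a second choice, because they overstate a low ICC.

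For the Hypothesis 3a mixed model, report the likelihood analysis of all observed waves without outcome imputation, as primary or at least as a sensitivity analysis. It is valid under missing at random and keeps the cluster structure intact. The plan already accepts the same reasoning where it allows full-information likelihood for its structural equation models.

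The cost is a few sentences in the SAP and a multilevel imputation routine. The downside is longer run time and possible convergence work.
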